Safety and effectiveness of apixaban in very elderly patients with NVAF compared to warfarin using administrative claims data

PFIZER CONFIDENTIAL

Page 1 of 23

NON-INTERVENTIONAL (NI) STUDY PROTOCOL

Study information

| | Orfetered offerthere are of entirely a |
|----------------------------------|--|
| Title | Safety and effectiveness of apixaban in very |
| l itie | elderly patients with NVAF compared to |
| Drate e el recordo en | warfarin using administrative claims data |
| Protocol number | B0661181 |
| Protocol version identifier | Ver. 2.0 |
| Date | 10-AUG-2023 |
| | B : Blood and blood forming organs |
| A stine substance | B01: Antithrombotic agents |
| Active substance | B01A : Antithrombotic agents B01AF: Direct factor Xa inhibitors |
| | - |
| | B01AF02: apixaban |
| | |
| Medicinal product | Eliquis (apixaban) |
| | |
| | |
| | Japan is a very elderly society compared to |
| | other countries in Europe and the United |
| | States, and many patients are newly |
| | diagnosed with NVAF even in their 80's or |
| | 90's. Most of these very elderly people have many complications and take many |
| | medications chronically as a result. In |
| | addition, many elderly patients have low body |
| | weight, sarcopenia, low ADL, frailty or frail-like |
| | characteristics, or high risk of falls. There has |
| | been much debate and inconclusive evidence |
| | on the value of anticoagulation for these very |
| Research question and objectives | elderly patients with NVAF. |
| | |
| | ARISTOTLE study has shown that apixaban is |
| | superior or equivalent to warfarin in various |
| | populations including higher risk populations. |
| | However, there are few evidence, especially |
| | on safety and effectiveness of apixaban |
| | versus warfarin. |
| | |
| | Objectives |
| | To investigate safety and effectiveness of |
| | apixaban compared to warfarin in very elderly |
| | patients with NVAF. In addition to the absolute |

| | age, effects on higher age-related risk factors on relative risk of apixaban to warfarin is also investigated. | |
|--------|--|---|
| Author | PPD Pfizer Japan Inc., [name] | , |

2. LIST OF ABBREVIATIONS

| Abbreviation | Definition |
|--------------|--|
| ADL | Activity of daily living |
| AF | Atrial fibrillation |
| CCI | Charlson comorbidity index |
| CV/MET | Cardiovascular/Metabolism |
| DPC | Diagnosis Procedure Combination |
| ICD | International Statistical Classification of Diseases and Related Health Problems |
| IPTW | Inverse Probability Treatment Weighting |
| MDV | Medical Data Vision |
| NVAF | Non-valvular atrial fibrillation |
| RWE | Real world evidence |

PFIZER CONFIDENTIAL

Page 6 of 23

4. PRINCIPAL INVESTIGATOR(S) OF THE PROTOCOLABSTRACT

- Title:
- Safety and effectiveness of apixaban in very elderly patients with NVAF compared to warfarin using administrative claims data
- Version 2.0, 10 AUG, 2023. PPD Japan Inc.

4.1. Rationale and background:

Japan is a very elderly society compared to other countries in Europe and the United States, and there are many very elderly patients wth NVAF who are treated with any of anticoagulant and there are considerable number of patients who are newly diagnosed with NVAF even in their 80's and 90's. Most of these very elderly people have many complications, including severe ones, and take many medications chronically.In addition, many elderly patients have low body weight, sarcopenia, low ADL, frailty or frail-like characteristics, or high risk of falls. There has been much debate and inconclusive evidence on the value of anticoagulation for these very elderly patients with NVAF.

Pfizer

ARISTOTLE study has shown that apixaban is superior or equivalent to warfarin in various populations including populations at higher risk. However, there are few studies in the real-world settings regarding very elderly patients who are at higher risk.

4.2. Study hypothesis and clinical questions

The ARISTOTLE study and various real-world evidence (RWE) have shown that apixaban is superior or equivalent to warfarin in safety and effectiveness profile. Subgroup analyses of the ARISTOTLE study suggested that superiority over warfarin could be consistent in most populations including high risk populations. Study hypothesis and clinical questions in this study is apixaban is superior to warfarin in both safety and effectiveness even in the very elderly patients with NVAF in the real-world settings.

The clinical question of this study is that apixaban has a superior effectiveness and safety profile compared to warfarin, even in very elderly patients who are at particularly high risk, such as those with CCI , frail or frail patients, CCI

4.3. Study objectives

The objective of this study is to investigate safety and effectiveness of apixaban compared to warfarin in very elderly patients with NVAF. CCI

4.4. Study design:

• This is a retrospective non-intervention observational study to evaluate the difference in safety and effectiveness between apixaban and warfarin using a database provided by Medical Data Vision Co. Ltd. (MDV Co. Ltd.). Eligible patients will be extracted from the database and allocated to the pre-defined cohorts based on the actual age, age of NVAF diagnosis and types of anticoagulant therapy.

• Based on the age category and anticoagulants on the index date (a date when patients initiated an anticoagulant for prevention of stroke/SE), eligible patients will be allocated to some cohorts. Patient characteristics will be balanced by an Inverse probability of treatment weighting (IPTW) method, and risk of stroke/SE (primary effectiveness endpoint) and major bleeding (primary safety endpoint) will be compared. Hazard ratios and 95% confident intervals will be calculated by using a COX proportional hazard method.

•

4.5. Population

 Patients registered in the MDV database from 26 February, 2013 to 31 December, 2021 will be used. First, atients with a NVAF diagnosis and received apixaban or warfarin as an anticoagulant after the NVAF diagnosis will be identified and then among them only patients who are 80 or older when they initiated these medications.

4.6. Variables – include exposures, outcomes, and key co-variates

• Following variables will be collected in this study at the index date (see 9.1 Study design for a definition of index date).

| | • Items | definitions | roles |
|---|--------------------------|--|-------------------------|
| ٠ | Gender | Male or female | Patient characteristics |
| • | CCI | | |
| • | Timing of NVAF diagnosis | 80-89 years ≥ 90 years | Patient characteristics |
| • | | | |
| • | Medications | Chronically prescribed medicinesDetails are shown in the SAP | Patient characteristics |
| • | | | |
| | | | |
| | | | |
| • | Stroke history | Previous diagnosis of cerebral infarction, cardiovascular embolism, hemorrhagic stroke, or TIM | Patient characteristics |

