9.2. Endpoints

- Primary effectiveness endpoint: stroke/SE (a composite of ischemic stroke, hemorrhagic stroke and SE)
- Primary safety endpoing: Major bleeding (any bleeding requiring hospitalization for treatment)

- Seconary effectiveness endpoint:
 - Cardiogenic embolic stroke
 - ➢ Ischemic stroke
- Secondary safety endpoint:
 - > Intracranial hemorrhage
 - Gastrointestinal bleeding
 - Intraocular bleeding

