7.1.2.1. Calculation of propensity score

Propensity scores will be estimated by calendar year of index date based on multivariable logistic regression analyses that incorporate potential predictors of therapy as independent variables in the regression and cohort status (prescription of warfarin or apixaban) as the outcome. Consecutive calendar years of index dates may be collapsed to build logistic regression model with robustness. The following covariates will be included in the logistic regression:

- age on index date
- age at NVAF diagnosis
- gender

PFIZER CONFIDENTIAL

- CHADS₂ score in baseline
- CHA₂DS₂-VASc score in baseline
- heart failure diagnosis in baseline
- coronary heart disease diagnosis in baseline
- peripheral arterial disorder diagnosis in baseline
- myocardial infarction diagnosis in baseline
- hyperthyroidism or thyrotoxicosis in baseline
- TIA diagnosis in baseline
- stroke or SE diagnosis in baseline
- renal dysfunction diagnosis in baseline
- liver dysfunction diagnosis in baseline
- bleeding diagnosis in baseline
- hypertension diagnosis in baseline
- diabetes mellitus diagnosis in baseline
- treated with antiplatelet drug in baseline
- treated with NSAIDs in baseline
- treated with gastric secretion inhibitor in baseline
- treated with statin-based drug in baseline
- treated with anti-hypertensives in baseline
- treated with anti-arrhythmics in baseline
- treated with beta-blockers in baseline
- treated with heparins in baseline
- cardioversion in baseline

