7.1.2.5. Calculation of hazard ratio with 95% confident intervals

Cox proportional hazards model will be used to compare endpoints in each of the sIPTW cohorts, with robust sandwich estimates to account for the clustering within balanced sets. The Cox proportional hazards model will include only index OAC treatment (apixaban or warfarin) as the independent variable if patient characteristics are well balanced between groups based on standardized difference in components of the PS. If not balanced, the unbalanced variable will be also included to the model in addition to the index OAC treatment. The hazard ratios with corresponding 95% confidence intervals and p-values will be reported.

PFIZER CONFIDENTIAL

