10.3.3. Stroke related medical history

Disease	ICD10 code	Standard disease code	Note
Homorrhago	160		
Hemorrhage stroke	l61		
SUDKE	162		Exclude non-traumatic extradural haemorrhage
	163		
		3489032	
		4371003	
		4379014	
Ischemic stroke		3448002	
		3448028	
		3489029	
		3489035	
		4379006	
	H340		
	G450		
TIA	G451		
	G458		
	G459		
	1740		Include only abdominal aortic embolism
	1741		Include only aortic embolism
	1742		Include only acute arterial occlusive disease of
	1/42		arteries of upper extremities
	1743		Include only femoral arterial occlusion and acute
Systemic			arterial occlusive disease of arteries of lower
embolism			extremities
	1744		
	1745		Include only iliac artery embolism
	1748		Include only hepatic artery embolism
	1749		Include only thromboembolism, embolic infarction, aortic embolism
	1748		Include only subclavian artery stenosis

10.3.4. bleeding

Procedure for definition of "bleeding"

Step 1. To extract the following group A or group B from MDV data base.

Group A: ICD-10 name includes "出血 (bleeding)" or "血腫 (ecchymoma)"

Group B: Disease name includes "出血 (bleeding)" or "血腫 (ecchymoma)"

Step 2. To select disease names considered to be relevant to side effect of OAC individually from disease names excluded in Step 1.

Step 3. To exclude disease names which are not considered to be relevant to side effect of OAC from the disease names included in Step 1.

ICD-10	ICD10Name
A162	Tuberculosis of lung, without mention of bacteriological or histological confirmation
A165	Tuberculous pleurisy, without mention of bacteriological or histological confirmation

ICD-10	ICD10Name				
B303	Acute epidemic haemorrhagic conjunctivitis (enteroviral)				
D500	Iron deficiency anaemia secondary to blood loss (chronic)				
D62	Acute posthaemorrhagic anaemia				
D66	Hereditary factor VIII deficiency				
D683	Haemorrhagic disorder due to circulating anticoagulants				
D698	Other specified haemorrhagic conditions				
D699	Haemorrhagic condition, unspecified				
E078	Other specified disorders of thyroid				
E274	Other and unspecified adrenocortical insufficiency				
G361	Acute and subacute haemorrhagic leukoencephalitis [Hurst]				
G951	Vascular myelopathies				
G968	Other specified disorders of central nervous system				
H052	Exophthalmic conditions				
H113	Conjunctival haemorrhage				
H168	Other keratitis				
H208	Other iridocyclitis				
H210	Hyphaema				
H313	Choroidal haemorrhage and rupture				

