H350	Background retinopathy and retinal vascular changes				
H356	Retinal haemorrhage				
H357	Separation of retinal layers				
H405	Glaucoma secondary to other eye disorders				
H431	Vitreous haemorrhage				
H448	Other disorders of globe				
H470	Disorders of optic nerve, not elsewhere classified				
H603	Other infective otitis externa				
H669	Otitis media, unspecified				
H738	Other specified disorders of tympanic membrane				
H922	Otorrhagia				
1213	Acute transmural myocardial infarction of unspecified site				
1230	Haemopericardium as current complication following acute myocardial infarction				
1312	Haemopericardium, not elsewhere classified				
1600	Subarachnoid haemorrhage from carotid siphon and bifurcation				
1601	Subarachnoid haemorrhage from middle cerebral artery				
1602	Subarachnoid haemorrhage from anterior communicating artery				
1603	Subarachnoid haemorrhage from posterior communicating artery				
1604	Subarachnoid haemorrhage from basilar artery				
1605	Subarachnoid haemorrhage from vertebral artery				
1606	Subarachnoid haemorrhage from other intracranial arteries				
1607	Subarachnoid haemorrhage from intracranial artery, unspecified				
1608	Other subarachnoid haemorrhage				
1609	Subarachnoid haemorrhage, unspecified				

ICD-10	ICD10Name				
l610	Intracerebral haemorrhage in hemisphere, subcortical				
l611	Intracerebral haemorrhage in hemisphere, cortical				
l613	Intracerebral haemorrhage in brain stem				
l614	Intracerebral haemorrhage in cerebellum				
1615	Intracerebral haemorrhage, intraventricular				
l616	Intracerebral haemorrhage, multiple localized				
l618	Other intracerebral haemorrhage				
1619	Intracerebral haemorrhage, unspecified				
1620	Subdural haemorrhage (acute)(nontraumatic)				
l621	Nontraumatic extradural haemorrhage				
1629	Intracranial haemorrhage (nontraumatic), unspecified				
1638	Other cerebral infarction				
1690	Sequelae of subarachnoid haemorrhage				
1691	Sequelae of intracerebral haemorrhage				
1780	Hereditary haemorrhagic telangiectasia				
1788	Other diseases of capillaries				
1841	Internal hemorrhoid with other complications				
1844	External hemorrhoid with other complications				
1848	Unspecified hemorrhoid with other complications				
1850	Oesophageal varices with bleeding				
1864	Gastric varices				
J041	Acute tracheitis				
J339	Nasal polyp, unspecified				
J90	Pleural effusion, not elsewhere classified				
J942	Haemothorax				
J950	Tracheostomy malfunction				

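### Prior hemorrhagic stroke enters the propensity score only through a pooled stroke/SE term and a broad bleeding term, so it is only partly controlled and its own balance is not assured

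*Protocol*

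**What the plan says.** - **Protocol 4.6** has one descriptive stroke-history item: "Previous diagnosis of cerebral infarction, cardiovascular embolism, hemorrhagic stroke, or TIM" (the last entry is as printed).
- **SAP 7.1.2.1** lists the propensity-score covariates. Three bear on this point: "TIA diagnosis in baseline", "stroke or SE diagnosis in baseline" and "bleeding diagnosis in baseline". No listed term is specific to hemorrhagic or to ischemic stroke. CHADS2 and CHA2DS2-VASc are also listed, but SAP 5.4 builds both from a combined stroke-or-TIA component.
- **Meaning of stroke/SE.** Protocol 9.2 defines the endpoint as "stroke/SE (a composite of ischemic stroke, hemorrhagic stroke and SE"), and SAP 5.1.1 agrees. The baseline term is not defined separately. The code table "10.3.3. Stroke related medical history" has separate rows for hemorrhagic stroke, ischemic stroke, TIA and systemic embolism. That the baseline term covers hemorrhagic stroke is therefore an inference, though a sound one.
- **SAP 10.3.4 and 10.3.5** give the bleeding codes. They include subarachnoid, intracerebral and subdural hemorrhage, for example "Intracerebral haemorrhage, unspecified", alongside epistaxis, hematuria, ecchymoses and fecal occult blood.
- **SAP 7.1.2.2** assesses the baseline covariates after weighting, with a 10% limit on the standardized difference.
- **SAP 7.1.2.5** adds a variable to the Cox model only if balance fails, "based on standardized difference in components of the PS".

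**The concern.** Two patients can look identical on the stroke and bleeding flags and yet differ in what matters here. One has had a hemorrhagic stroke. The other has had an ischemic stroke and, separately, a nosebleed. These histories may steer the choice between apixaban and warfarin differently, and they plausibly carry different risks of intracranial bleeding.

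That outcome counts three times: as hemorrhagic stroke within primary stroke/SE, as hospitalized bleeding within primary major bleeding, and as the secondary intracranial hemorrhage endpoint. If prior hemorrhagic stroke influences drug choice in its own way, some confounding survives the weighting. A larger database narrows the interval around that bias but does not remove it. The pooled flags can also look well balanced while the component is not.

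**Working it through.** **Plan figures.** The documents give no prevalence, drug-choice effect or risk ratio for prior hemorrhagic stroke, so there is no plan figure to reproduce on this point. The sample-size table (SAP 4.5) does reproduce: 4(1.96 + 0.84)²/(ln 0.59)² gives 113 events and 113/0.0184 = 6,141 patients; a hazard ratio of 0.53 gives 78 events and 78/0.0145 = 5,379. It is used below only for its hazard ratios, as a scale.

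**Assumed inputs (none from the documents).** Prior hemorrhagic stroke H: 1-4%. Ischemic stroke I: 20%. Other bleeding B: 12%. The three are independent. About 55% receive apixaban. H multiplies the odds of apixaban by 2 or 0.5; I and B do not affect drug choice. There is no drug effect. H multiplies the event rate by k = 4 (major bleeding) or k = 8 (intracranial hemorrhage).

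**Method.** Exact cell probabilities, without sampling:

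1. Form the plan's two flags: stroke = I or H; bleeding = B or H.
2. Fit a main-effects logistic score on those flags and apply inverse-probability weights.
3. Read off the weighted shares of H: m1 (apixaban) and m0 (warfarin).
4. Standardized difference = (m1 − m0)/√{[m1(1 − m1) + m0(1 − m0)]/2}.
5. Bias factor on the rate ratio = [1 + (k − 1)m1]/[1 + (k − 1)m0].

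**Why control is partial.** At H = 2%, the cell with both flags on holds 2% with H plus 0.98 × 0.20 × 0.12 = 2.35% without it, so H is 2/4.35 = 46% of that cell. The main-effects fit is also pulled toward the larger single-flag cells.

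**Worked case, H = 2%, odds ratio 2.** The shares are 2.57% vs 1.30% before weighting and 2.44% vs 1.39% after.

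- Standardized difference: 0.0105/0.137 = 0.077, under the 10% limit. Both pooled flags are below 0.001.
- k = 4: (1 + 3 × 0.0244)/(1 + 3 × 0.0139) = 1.0732/1.0417 = 1.03.
- k = 8: (1 + 7 × 0.0244)/(1 + 7 × 0.0139) = 1.1708/1.0973 = 1.07.

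**Ends of the range.**

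| H | Odds ratio | m1 vs m0 after weighting | k = 4 | k = 8 |
|---|---|---|---|---|
| 1% | 2 | 1.25% vs 0.67% | 1.02 | 1.04 |
| 4% | 2 | 4.71% vs 2.94% | 1.05 | 1.10 |
| 1% | 0.5 | 0.72% vs 1.32% | 0.98 | 0.96 |
| 4% | 0.5 | 3.10% vs 4.90% | 0.95 | 0.91 |

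The absolute standardized differences run from about 0.06 to 0.09. With separate terms for I, H and B they are 0.000 and every factor is 1.000.

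**Wider range.** With H 1-6%, other bleeding 8% and odds ratios 1.5-3, the residual standardized difference is 0.034-0.138. It exceeds 0.10 in 3 of 12 scenarios (odds ratio 3 with H at 2% or more). The factor is 1.003-1.109 for 2- to 5-fold event risk.

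**The case against.** - **No imbalance is shown.** This stands. A reader might infer that prior hemorrhagic stroke will be unbalanced between the cohorts. The documents support only that its balance is not assured. It generally sets both flags, so it is partly controlled.
- **The propensity score does not carry the Protocol 4.6 item.** This stands. In the SAP, TIA is separate and SE is added. The protocol item shows the same pooling in a descriptive variable; the point rests on the SAP 7.1.2.1 list.
- **The plan may check it after all.** This stands in part. A reader might infer that no balance check looks at hemorrhagic stroke. SAP 7.1.2.2 refers to the baseline covariates generally, and parts of the SAP 5.4 table are blacked out, so this cannot be settled. The trigger in SAP 7.1.2.5 is legible and tied to score components, and the legible component list has no hemorrhagic-stroke term.
- **Other covariates help.** True, but modestly. In one illustration, antiplatelet use was assumed at 60% after ischemic and 10% after hemorrhagic stroke; adding it cut the residual standardized difference from 0.055 to 0.048.
- **The inputs are assumed and the effect is small.** This stands. Score terms refer to the 180-day baseline, and patients treated in a contraindicated manner are excluded, so even 1-4% is uncertain. Against the planning hazard ratio of 0.59 for major bleeding, factors of 0.95-1.05 give 0.59 × 0.95 = 0.56 to 0.59 × 1.05 = 0.62.
- **E-values are planned (SAP 7.2.3).** At 0.59 and 0.53 they would be about 2.8 and 3.2, which puts a bias of this size in proportion. But they address unmeasured confounding, and this variable is already coded.

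**Conclusion.** The point holds in a limited form. In the listed propensity score, prior hemorrhagic stroke is represented only through two pooled flags. It is partly controlled, its own balance is not assured, and the Cox-adjustment rule cannot respond to it.

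Under the assumed inputs, the residual bias factor is about 1.02-1.05 or 0.98-0.95 at 4-fold event risk, and 1.04-1.10 or 0.96-0.91 at 8-fold risk. The direction is unknown because it depends on which drug these patients tend to receive. This would not overturn effects of the planned size on the primary endpoints. It matters most for intracranial hemorrhage. No separate figure is offered for stroke/SE, since the risk multiplier for that composite is unknown; at 2-fold risk and 2% prevalence the factor would be 1.0244/1.0139 = 1.01.

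The change is worth making because it removes an avoidable source of confounding at almost no cost, not because a material bias has been demonstrated.

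**What to change.** In SAP 7.1.2.1:

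1. Replace the pooled stroke/SE term with three terms built from the SAP 10.3.3 codes: ischemic stroke, hemorrhagic stroke and systemic embolism.
2. Keep a bleeding term, defined as bleeding other than hemorrhagic stroke.
3. Report the standardized difference of each term after weighting. As score components they then fall under SAP 7.1.2.5 without further wording.

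The first step is the essential one. In the worked case the residual standardized difference was 0.077, so a 10% check alone would have passed it.

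The cost is a few lines of SAP text and two more terms per propensity model, with no new data. The small downside is sparse cells in some calendar years, which the existing provision for collapsing consecutive years handles.

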4.7. Data sources

Medical Data Vision database, commercially available administrative claims database from hospitals introducing DPC (Diagnosis Procedure Combination) system, which comprises administrative data pertaining to approximately 39 million individuals (as of 2021 Dec.) managed in the inpatient and outpatient settings.

4.8. Study size

All eligible patients will be used for the analysis. The number of patients to be used for the analysis was estimated in the preliminary feasibility check and we have confirmed that the statistical power may be sufficient to the analysis.

Roughly estimated number of patients are as follows,

- Male with NVAF: \geq 80: 34,157
- Female with NVAF: \geq 80: 33,163

The number of patients who are newly diagnosed with NVAF in 80-89 or \ge 90 are not known.

The dealied results of estimation of power calculation will be described in the Statistical Analysis Plan (SAP)

